Results of this proposal will be used to support an application for extramural funding at the end of this funding period.

Approach (Figure 1): Volunteers with type 2 diabetes and obesity who are scheduled to undergo RYGB as part of their clinical care will be studied immediately prior to surgery and at 12 weeks post-operatively using a labeled mixed meal to enable simultaneous measurement of glucose metabolism and insulin secretion and

action [10]. Blood samples for targeted metabolic profiling will also be drawn. A fecal sample to characterize the microbiome will be collected at both visits. A matched control group of subjects with type 2 diabetes and obesity who are not scheduled to undergo bariatric surgery will also be recruited and studied at baseline and 12 weeks following caloric restriction similar to that required post-operatively after RYGB. We will utilize weekly meetings with a dietician and a psychologist to ensure compliance with the prescribed diet.

The overall objective of this proposal is to form the basis of a line of investigation that will underpin my research career and future extramural funding. We will address the following specific aims: -

Specific Aim 1: Characterize the changes in the circulating metabolome that occur after Roux-en-Y Gastric Bypass in contrast to caloric restriction alone.

Hypothesis: *Metabolomic changes after Roux-en-Y gastric bypass surgery are associated with a decrease in endogenous glucose production in subjects with type 2 diabetes.*

Specific Aim 2: Characterize the changes in gut microbiome in subjects with type 2 diabetes after Roux-en-Y gastric bypass, in contrast to caloric restriction alone.

Hypothesis: *Gut microbiome changes unique to Roux-en-Y gastric bypass influence remission of type 2 diabetes.*

Preliminary Studies

A. Mathematical modelling of glucose turnover.

The meal minimal model can measure insulin secretion and action [11, 12] [13] and has been validated using hyperglycemic and euglycemic clamps as well as tracer infusions to directly measure glucose turnover. We have shown that insulin sensitivity (S_i) and β -cell responsiveness (ϕ) can be estimated from measured glucose and C-peptide concentrations [12, 14]. The appropriateness of insulin secretion for the prevailing degree of insulin action is assessed by calculating the total disposition index (DI_{total}), which equals the product of insulin secretion and insulin sensitivity ($\phi_{total} \times S_i$).

[figure not shown]

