Study Subjects: Individuals aged 20-65 years seen for weight management in the Nutrition Clinic at the Mayo Clinic, will be recruited to the study prior to undergoing Roux-en-Y Gastric Bypass (RYGB). We will recruit 15 subjects who have a fasting glucose concentration of ≥ 126 mg/dl on two or more occasions or who have a history of type 2 diabetes or impaired fasting glucose treated with one or two oral agents other than thiazolidinediones. Potential participants will attend the Mayo Clinic Clinical Research Trial Unit (CRTU) for a screening visit. In addition, we will also recruit 15 subjects with type 2 diabetes or impaired fasting glucose who are **not** interested in pursuing surgical intervention but are willing to undergo supervised caloric restriction as detailed below. The 2 groups will be matched for age, gender and BMI and duration and severity (HbA_{1c} and no. of oral medications needed to achieve glycemic control) of diabetes.

Exclusion Criteria: Subjects <20 years of age will not be studied to minimize the possibility of type 1 diabetes. Subjects > 65 years of age will not be studied to minimize the potential confounding effects of age on glucose tolerance. Subjects on chronic antibiotic therapy will be excluded due to their influence on gut bacteria. Subjects will refrain from using antibiotics for 2 weeks prior to the screening visit until completion of the study, except for routine peri-operative use and as clinically indicated. Healthy status will indicate that the participant has no known active systemic illness and no active microvascular or macrovascular complications of their diabetes.

Screening Visit: Subjects will provide written informed consent and undergo a history and physical examination along with blood collection for complete blood count, fasting glucose, HbA_{1c} and chemistry group; urine collection to exclude infection, proteinuria or pregnancy and ECG. Subjects will ensure that they have not taken any antibiotics for 2 weeks prior to the screening visit. The Minnesota Leisure-Time Physical Activity questionnaire will be administered to assess habitual activity levels [19]. They will be given instructions on managing their diabetes medications. Subjects will also complete the validated bowel disease questionnaire to ensure that there are no functional or organic bowel symptoms [20]. A receptacle to collect a baseline fecal sample prior to Study 1 will be provided to subjects.

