Body Composition: Body composition will be measured at the screening visit using dual-energy X-ray absorptiometry (iDXA scanner; GE, Wauwatosa, WI) and abdominal CT Scan with cuts at L2/3 and T11/12 to determine percent body fat and visceral fat [21].

Experimental Design: Subjects will be studied on two occasions, the second study will occur approximately 12 weeks after Roux-en-Y gastric bypass or equivalent caloric restriction.

Study 1 (baseline): All subjects will be admitted to the Mayo Clinic CRTU at 17.00 hours the evening before the study. A fecal sample, produced within 48 hours of the start of the study, will be collected. Following ingestion of a standardized low calorie meal (197 Kcal: 40% carbohydrate, 30% fat, and 30% protein) subjects will fast overnight. The meal will occupy a volume that is tolerable to patients who have undergone restrictive upper gastrointestinal procedures. Approximately at 05:30 a cannula will be inserted retrogradely into a vein of the dorsum of the hand. This will be placed in a heated Plexiglas box maintained at 55°C to allow sampling of arterialized venous blood. A cannula will also be placed in the vein of the contralateral hand to allow infusion of tracers. Approximately at 06:30 hrs (-180 minutes) subjects will receive a primed continuous infusion of [6,6-²H₂] glucose. At the start of the study, approximately 09:30 hrs (0 minutes) subjects will consume a mixed meal consisting of one scrambled egg, 55g of ham), and Jell-O containing 35g of glucose enriched with [1-¹³C] glucose (to~4%) as previously described. An infusion of [6-³H] glucose will be started at the same time at a rate that mimics the anticipated glucose appearance of the [1-¹³C] glucose contained within the meal. At the same time, the rate of infusion of the [6,6-²H₂] glucose will be altered so as to approximate the anticipated pattern of fall in endogenous glucose production as previously described in detail [21-23]. Blood will be collected to allow measurement of glucose, tracer and hormone concentrations. At the end of the study (15:30, 360 minutes), the cannulae will be removed; participants will consume a late lunch and leave the CRTU.

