1. **Endogenous Glucose Production:** Based on data from previous studies [27-29], 15 subjects per group would provide approximately 80% power to detect a 25% difference in nadir EGP values and 87% power to detect a 25% difference in integrated EGP values.
2. **Disposition Index:** 15 subjects per group would provide approximately 80% power to detect an association of intervention type corresponding to a 35% difference in mean DI values relative to the overall mean [28, 30].
3. **Alpha-Aminoadipic Acid:** 15 subjects per group would provide approximately 90% power to detect a 15% difference in mean values.

Interpretation. In the RYGB group, if the improvements in glucose metabolism are associated with a metabolomic signature that is unique, then we will accept our primary hypothesis that metabolomic changes after surgery are associated with a decrease in endogenous glucose production in subjects with type 2 diabetes. We will be able to differentiate between changes in insulin secretion (ϕ_{total}), insulin action (Si) and DI to determine the mechanistic basis for the observed improvements. If the improvements in glucose metabolism are associated with a unique change in the gut microbiome, then we will accept our secondary hypothesis that unique changes in the gut microbiome influence remission of type 2 diabetes. We will specifically be looking for metabolomic markers of the gut microbiome, which have been shown to influence insulin sensitivity [8, 9] and energy harvest, such as short-chain fatty acids [31].

Limitations. Changes in the gut microbiome and circulating metabolome are influenced by dietary intake. Our study design is such that both groups will have similar, but not identical macronutrient composition of their meals. We will minimize differences by utilizing a registered dietician as well as a clinical psychologist to help ensure compliance with the prescribed diet and discourage food consumption outside of what is provided by the study.

Future Directions. Identification of a unique metabolomic profile after RYGB will permit manipulation of concentrations of these substances in overweight subjects with type 2 diabetes to determine their effect on weight loss and glucose metabolism. I hope to use the results of this study to secure extramural funding at the end of this award and be able to continue working on the role of bariatric surgery in the amelioration of type 2 diabetes.

Human Subjects

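### Peri-operative antibiotics fall only in the RYGB arm, between its two stool samples, and nothing planned lets the Aim 2 acceptance rule separate them from the surgery

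*Combined protocol and SAP*

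**What the plan says.** The protocol itself treats antibiotics as a threat to the microbiome measurement. Under Exclusion Criteria: "Subjects on chronic antibiotic therapy will be excluded due to their influence on gut bacteria". The same paragraph has the remaining participants "refrain from using antibiotics for 2 weeks prior to the screening visit until completion of the study", but with a carve-out: "except for routine peri-operative use and as clinically indicated". The Screening Visit section repeats the look-back at entry: "Subjects will ensure that they have not taken any antibiotics for 2 weeks prior to the screening visit".

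On timing, the Approach paragraph says that surgical participants "will be studied immediately prior to surgery and at 12 weeks post-operatively", and that "A fecal sample to characterize the microbiome will be collected at both visits". Study 1 (baseline) adds one condition on the stool sample: "A fecal sample, produced within 48 hours of the start of the study, will be collected". Study 2 is described as identical to Study 1. Neither section sets a minimum time since the last antibiotic dose.

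On analysis, Calculations says only that between-group differences in the microbiome will be quantified. Statistical Analysis describes an analysis of covariance, with age, gender and change in BMI or lean body mass as example covariates. Limitations names diet as the influence on the microbiome and metabolome. The decision rule for Aim 2 is under Interpretation: "If the improvements in glucose metabolism are associated with a unique change in the gut microbiome, then we will accept our secondary hypothesis". That hypothesis is that microbiome changes unique to RYGB influence diabetes remission.

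**The concern.** Aim 2 depends on the word unique: a change seen after RYGB and not after equivalent caloric restriction is to be read as belonging to RYGB. That needs the arms to differ, between the two stool samples, in the surgery and in nothing else known to alter gut bacteria. The protocol names antibiotics as something that does, then permits them around the operation in one arm only. It also permits treatment courses in either arm, with no provision for one that ends shortly before a stool sample.

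At stake is what Aim 2 can conclude. If an antibiotic effect contributes to the RYGB arm's change, the rule as written would credit it to the bypass and carry it forward as a mechanism of remission. The reference list makes this more than a formal worry. One source cited for microbiome effects on insulin sensitivity (reference 8) is, by its title, a mouse study in which altering gut bacteria with antibiotics improved insulin signalling. Only the title is available here, and it is animal work.

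**Working it through.** The plan gives no figure to reproduce. Its power statements cover endogenous glucose production, disposition index and alpha-aminoadipic acid, not the microbiome. The check is of the text, with one illustration.

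**1. Who can be exposed.** Only the RYGB arm has an operation, so the peri-operative exception applies to one arm. The clinical-indication exception applies to both. Potential Risks (Vascular catheter placement) also allows antibiotics for phlebitis in either arm. In the order in which Study 1 sets out its steps, cannulae go in after stool collection, so such a course would also fall between samples. Four RYGB participants have a further infusion study in postoperative week 4 (Exendin-(9,39) Amide Study), one more catheter occasion in that arm only.

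**2. When.** The first RYGB sample is taken just before surgery and the second in the 12th postoperative week. Peri-operative antibiotics therefore lie between them. A clinically indicated course can occur at any time up to Study 2.

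**3. What would detect or handle it.**
- Antibiotic-free check: at screening only. The duty to abstain continues to study end, but nothing is said about a sample that follows a permitted course.
- Record of agent and dates: none described.
- Covariate: antibiotics are not among the examples, though the list is open.
- Sensitivity analysis: none described.
- Limitations: diet only.

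**4. Could a covariate separate the two effects?** Inputs: 15 participants per arm (Study Subjects). Assumption: all 15 RYGB participants receive peri-operative antibiotics; the protocol calls this use routine but gives no rate. Let c be the number of CR participants exposed between samples. The documents do not give c, so a range is shown.

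The squared correlation between arm and exposure is

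φ² = [15(15 − c)]² / [15 · 15 · (15 + c)(15 − c)] = (15 − c)/(15 + c).

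The variance of the adjusted arm effect is inflated by

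1/(1 − φ²) = (15 + c)/(2c).

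- c = 0: φ² = 1; exposure and arm are the same variable and cannot be separated.
- c = 1: 16/2 = 8.0
- c = 2: 17/4 = 4.25
- c = 3: 18/6 = 3.0

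If fewer than 15 RYGB participants are exposed, the overlap is less complete and the inflation smaller.

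**5. Does the plan's own 2-week interval solve it?** Not for peri-operative use. A course around surgery is about 12 weeks before the Study 2 sample, so it clears a 2-week condition by about 12 − 2 = 10 weeks. The interval bears only on courses close to a sample.

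**6. Scale of one late course.** One affected participant is 1/15 = 6.7% of an arm's participants. One affected sample is 1/30 = 3.3% of an arm's two-visit samples. A change score needs both samples, so setting one aside loses one of 15 changes. Neither percentage measures bias.

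**The case against.** Several stronger readings are tempting, and the documents do not support them.

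- A reader might infer that the antibiotic rule applies only at screening. It does not: abstention runs to study completion and so covers both samples. The gap is limited to what follows a permitted course.
- A reader might infer that any RYGB-only change will be accepted. Interpretation also requires an association with improved glucose metabolism. That condition does not remove the problem. Pooled across arms, surgery, its antibiotics and the glucose improvement go together. Within the RYGB arm, an exposure shared by all could not by itself create a correlation, but uniqueness would still be judged against an arm that had no operation. The plan does not say which analysis is meant.
- A reader might infer that the plan requires recently treated participants to stay in the analysis. No microbiome analysis set is defined, and the covariate list is open. Handling is unspecified, not prescribed.

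Two further objections carry weight. First, surgery here is part of clinical care, so RYGB against CR can be read as a comparison of care packages that include routine prophylaxis. On that reading the comparison is valid, but its conclusion concerns the package, which is the narrower attribution sought here. Second, about 12 weeks separate peri-operative use from the second sample, and the effect may have gone by then. That stands as an uncertainty. It argues for a modest grading, not for leaving antibiotics out of Limitations. Clinically indicated courses may have no such delay.

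Excluding treated participants from the main comparison would also be open to question: antibiotic use arises after baseline and may follow from surgery, so exclusion could select unequally from arms of 15.

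**Conclusion.** The concern holds in a limited form. Peri-operative antibiotics occur only in the RYGB arm and between its two stool samples. Permitted courses in either arm carry no pre-sample interval. No record, sensitivity analysis or stated limitation addresses either. The Aim 2 rule therefore cannot distinguish an effect of RYGB from an effect of antibiotics.

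The size of any bias cannot be computed from the documents. Complete overlap, 15 of 15 against 0 of 15, is an assumption; with a few CR participants exposed, adjustment becomes possible but imprecise. It would be wrong to go further and say that an observed microbiome change would be an antibiotic artefact, because the documents do not show whether a peri-operative effect persists at 12 weeks.

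This is a cheap improvement that narrows what Aim 2 may claim. It does not touch the three comparisons for which power is given.

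**What to change.** - Record the agent, start date and stop date of every antibiotic from screening to Study 2, in both arms.
- Keep all samples in the main microbiome comparison.
- Add two sensitivity analyses: (a) excluding any stool sample taken within 2 weeks of an antibiotic, the interval the protocol already uses at screening; (b) excluding participants with any non-peri-operative course between their two samples. Judge agreement by the direction and size of the estimates with their intervals, since the numbers will be smaller.
- Reword the rule under Interpretation so that an RYGB-only change is attributed to surgery together with its routine peri-operative antibiotics, and only if it holds in both analyses.
- Name antibiotics beside diet under Limitations, and state that neither sensitivity analysis removes peri-operative exposure; only the rewording deals with that.

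None of this alters when antibiotics may be given. The cost is one data field, two short analyses with some loss of precision, possible selection in those analyses because antibiotic use is post-baseline, and a narrower Aim 2 conclusion.

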Microbiome Laboratory. The microbiome lab in the Medical Sciences Building at Mayo Clinic houses 2 computers containing 32-core AMD processors and 64 GB of RAM on which the calculations and modeling proposed will be carried out. The DNA extraction and library preparation facility includes a FastPrep 24 beadbeater, 2 PCR machines, a qPCR machine, a biosafety cabinet, automated and manual gel electrophoresis, and all other equipment and reagents necessary for DNA extraction and 16S rDNA amplification. The Medical Genomics Facility houses 6 Illumina Hi-Seq, 2 Illumina Mi-Seq, Sanger, and Pac-Bio sequencers.

Calculations: Insulin sensitivity (S), β -cell responsivity indices and total disposition index (DI_{total}) will be calculated from plasma glucose and insulin concentrations using the "oral" glucose minimal model [26]. [6-³H] glucose will be used to trace the appearance of the ingested [1-¹³C] glucose and [6,6-²H₂] glucose will be used to trace endogenous glucose production. As previously described, meal appearance will be calculated by multiplying the systemic rate of appearance of [1-¹³C] glucose by the [1-¹³C] glucose in the meal [10]. In addition to measurement of peak hormone concentrations, we will calculate area above basal for the first 2 hours and for all 6 hours after meal ingestion using the trapezoidal rule as previously described [27]. Differences in the metabolomic profile between groups will be quantified. Differences in the microbiome profile between groups will be quantified.

We will subsequently explore correlations between changes in glucose metabolism and multiple metabolites. The metabolome and microbiome analysis will be undertaken in close collaboration with the bioinformatics core ([name], Ph.D.) to examine qualitative and quantitative differences as well as undertake pathway analysis to potentially identify specific pathways affected uniquely by CR or RYGB.

Statistical Analysis. We will examine between-group (RYGB vs. CR) differences from the baseline study to the post-intervention study (Study 2- Study 1). To do so we will utilize an analysis of covariance adjusting for relevant covariates (e.g. age, gender and change in BMI or lean body mass after surgical intervention) as previously described. We will primarily examine between group differences in:

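### The rule for accepting the primary hypothesis is broader than the hypothesis (glucose metabolism rather than EGP) and rests on an exploratory correlation search with no stated error control or power

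*Combined protocol and SAP*

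**What the plan says.** - **Hypothesis (Specific Aim 1).** "Metabolomic changes after Roux-en-Y gastric bypass surgery are associated with a decrease in endogenous glucose production" in people with type 2 diabetes.
- **Acceptance rule (Interpretation).** The condition, set for the surgical arm, reads: "if the improvements in glucose metabolism are associated with a metabolomic signature that is unique, then we will accept our primary hypothesis". Its outcome is glucose metabolism in general. The claim accepted when it is met concerns EGP: "then we will accept our primary hypothesis that metabolomic changes after surgery are associated with a decrease in endogenous glucose production". The same paragraph separates insulin secretion, insulin action and DI as possible mechanisms.
- **Association analysis (Calculations).** "We will subsequently explore correlations between changes in glucose metabolism and multiple metabolites". The number of metabolites, the arm or arms used, the coefficient and the threshold are not given. The same paragraph also plans to "undertake pathway analysis to potentially identify specific pathways affected uniquely by CR or RYGB".
- **Inferential model (Statistical Analysis).** Analysis of covariance on change from Study 1 to Study 2, RYGB against caloric restriction (CR). "We will primarily examine between group differences in" three quantities: EGP, DI and alpha-aminoadipic acid.
- **Power (Statistical Analysis, items 1–3).** With 15 per group: for EGP, "80% power to detect a 25% difference in nadir EGP values and 87% power to detect a 25% difference in integrated EGP values"; for DI, 80% for a 35% difference; for alpha-aminoadipic acid, 90% for a 15% difference.
- **Use of the result (Future Directions).** "Identification of a unique metabolomic profile after RYGB will permit manipulation of concentrations of these substances" in later work.

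**The concern.** The rule has two halves: the signature is unique to RYGB, and within RYGB it goes with the improvement in glucose metabolism. The between-arm comparisons and the pathway analysis can speak to the first half. They cannot speak to the second, because two differences in arm means do not show that patients with the larger metabolite change are those with the larger fall in EGP. The second half therefore rests on a search that the plan itself calls exploratory, yet the plan accepts a primary hypothesis on it.

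The outcome side is open too. The hypothesis names EGP and the condition does not, so an association with DI alone would satisfy the rule and lead to a claim about EGP. Even within EGP, two measures are listed (nadir and integrated), and neither is chosen for the association.

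At stake is the study's main mechanistic conclusion and the choice of substances to manipulate next. The between-arm comparisons themselves are not affected.

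**Working it through.** **1. The plan's own powers.** They cannot be reproduced forwards, because neither the SDs nor the significance level is stated. Solved backwards (two-sample t test, two-sided 5%, 15 per group), they imply SDs, as a percentage of the mean, of 23.6 (nadir EGP), 21.4 (integrated EGP), 33.0 (DI) and 12.2 (alpha-aminoadipic acid). Nothing shows these powers to be wrong. All four are for a difference in means, and none is for a correlation.

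**2. Inputs for the illustration.**
- From the plan: 15 RYGB and 15 CR patients (Study Subjects).
- Inferred: correlations use RYGB alone, because the acceptance rule is set in that group. Calculations does not say.
- Assumed: 15 metabolites (rows of Table 1 as extracted), one EGP measure, two-sided 5%, normal data, no dropout, no true association, equal inter-metabolite correlation c from 0 to 0.7.

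**3. Threshold for one correlation.** r = t/√(n − 2 + t²), with t = 2.160 on 13 df: 2.160/√(13 + 4.67) = 0.514.

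**4. Association half alone.** For independent metabolites:
- At least one hit: 1 − 0.95^15 = 0.537.
- At least two hits: 1 − 0.95^15 − 15 × 0.05 × 0.95^14 = 1 − 0.463 − 0.366 = 0.171.

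Simulation extends this to correlated metabolites:

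| Counting rule | c = 0 | 0.3 | 0.5 | 0.7 |
|---|---|---|---|---|
| At least one p < 0.05 | 0.54 | 0.47 | 0.38 | 0.27 |
| At least two p < 0.05 | 0.17 | 0.17 | 0.17 | 0.15 |
| Benjamini-Hochberg at 5% | 0.05 | 0.05 | 0.05 | 0.04 |

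For at least one hit as c goes from 0 to 0.7, 5 metabolites give 23% to 16% and 30 metabolites give 79% to 37%.

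**5. Adding the uniqueness half.** Require the same metabolite to differ between arms at p < 0.05.
- If no metabolite truly differs: 1 − (1 − 0.05 × 0.05)^15 = 1 − 0.9975^15 = 0.037. Over the range of c this is about 4% to 3%.
- If 13 truly differ, each detected with probability d: 1 − (1 − 0.05d)^13 × 0.9975². At c = 0 this gives 0.284 (d = 0.5), 0.453 (d = 0.9) and 0.489 (d = 1). Over c = 0 to 0.7 the simulated ranges are 28–16%, 45–24% and 49–26%.

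The 13 is 15 minus the two changes (glycine and alanine) that Preliminary Studies C calls shared. It is an upper scenario, not an estimate.

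**6. Power at n = 15.** Simulation gives these figures:

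| True r | One pre-named metabolite | One true among 15 independent, Benjamini-Hochberg |
|---|---|---|
| 0.5 | 50% | 14% |
| 0.65 | 80% | about 40% |
| 0.8 | 98% | 83% |

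For r = 0.5, 80% power on a single test needs about 28 RYGB patients.

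**7. Two routes at once.** If alpha-aminoadipic acid at 5% and a false-discovery-rate (FDR) procedure over the metabolites could each establish the conclusion, false acceptance with independent metabolites is about 1 − 0.95 × 0.95 = 0.098. Simulation over c = 0 to 0.7 gives about 10% to 7%.

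**The case against.** **The rule does not say that one correlation is enough.** A reader might infer that a single nominally significant correlation leads to acceptance. The text does not support that. It speaks of a signature and gives no p-value, level or single-metabolite trigger. This stands: the defect is that the rule is undefined, and the 54–27% figure applies only to the most permissive definition.

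**Uniqueness screens out false leads.** It does when few metabolites differ between arms, and hardly at all when most do. Preliminary Studies C reports clear differences in amino acid profiles, but gives no count. Table 1, as far as it can be read, marks changes within each intervention. A change flagged in one arm and not in the other does not establish a difference between arms, so the table cannot be read as showing that 13 metabolites differ.

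**The correlations may pool both arms.** Possible. That would change the power figures, but not the missing error control.

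**Alpha-aminoadipic acid is pre-named.** It is, but for a difference in means and not for its correlation with EGP.

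**This is early work.** The results are meant to support a funding application, the correlations are called exploratory, and the next step would test any lead before it affected care. That lowers the stakes. It does not reconcile an exploratory search with acceptance of a primary hypothesis, or a condition on glucose metabolism with a claim about EGP.

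**Conclusion.** The concern holds in this form and should be fixed. Three parts rest on the text alone: the condition is wider than the hypothesis it decides; the only analysis of association has no stated error control or power; and *signature*, *associated* and the analysis group are left undefined.

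The size is illustrative. Depending on how many hits count, how many metabolites differ between arms and how strongly metabolites are correlated, false acceptance in the scenarios shown for 15 metabolites runs from about 3% to 54%. No single value in that range can be attributed to the plan. Nor do the documents show that the stated between-arm powers are wrong; those powers simply answer a different question.

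**What to change.** 1. **Outcome.** Make change in EGP the outcome of the acceptance rule and name one measure, nadir or integrated. Label associations with insulin secretion, insulin action and DI exploratory.
2. **Signature.** Define it as metabolites that change in RYGB and whose change differs from CR, with FDR control on the between-arm screen. Requiring only a difference between arms would admit a metabolite that changes under CR alone.
3. **Association.** State that the metabolite–EGP associations are tested in RYGB, by one governing route chosen in advance: either FDR control across all metabolites, or alpha-aminoadipic acid alone at 5% with all others exploratory. Do not let both support the primary conclusion.
4. **Conclusion.** Replace acceptance of the hypothesis with a statement that the data support an association. Report metabolite–EGP slopes by arm with confidence intervals. Do not call an association (as distinct from a signature) unique to RYGB without an arm-by-metabolite interaction. Make the same wording change in the parallel microbiome rule.

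**Cost.** Wording and minor analysis, with no new data. Fewer metabolites will be declared and power is low (step 6 of the working). The interaction is weaker still: at 15 per arm, simulated power is 26% for a correlation of 0.5 against 0, and 50% for 0.7 against 0. The report should say that a null result is uninformative.
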